The primary efficacy endpoint for all Phase 2 cohorts except for Cohort 2 is the complete response rate (CR + CRh), which will be tabulated by study phase, cohort, and dose based on the best overall response. Phase 2 Cohort 1 will test the complete response rate using a 1-sided exact binomial test for one proportion, with a 2.5% significance level. Other Phase 2 cohorts have different hypothesis tests, further described in Section 9.2.2. Additionally, the ORR will be calculated for each cohort, presented with the corresponding 95% confidence intervals, based on exact binomial methods. Number and percentage of patients within other response categories will also be presented by dose/dosing schedule and visit.

The primary efficacy endpoint for Phase 2 Cohort 2 is 4-month RFS, further described in Section 9.2.4.3.

Analyses of DOR, TTR, EFS, RFS, and OS will be based on Kaplan-Meier methods for each cohort; the median time will be tabulated along with the 95% confidence intervals.

Safety Analyses:

All safety analyses will be descriptive in nature and based on the Safety Set.

Number of DLTs, based on the DLT-Evaluable Set, will be summarized by dose level.

Safety data, including adverse events, safety laboratory values, vital signs, physical examination findings, and ECG results, will be based on the Safety Set, summarized by study stage and phase and by dose, and listed in the individual data listings as appropriate.

For selected safety parameters, National Cancer Institute Common Terminology Criteria for Adverse Events (MedDRA version 19.1) grades and the corresponding shift from baseline grade may be evaluated, based on the Safety Set, if available data permit.

Additional efficacy and safety analyses will be specified in the Statistical Analysis Plan.

TABLE OF CONTENTS

LI	ST OF TA	ABLES	23
LI	ST OF FI	GURES	23
LI	ST OF A	PPENDICES	23
AI	BREVIA	ATIONS	24
1	BACKO	ROUND	27
	1.1 I	Pharmacology	27
	1.2	Toxicokinetics	27
	1.3 I	Enzyme-Mediated Drug-Drug Interaction Potential	28
	1.4	Toxicology	28
	1.5	Clinical Rationale	29
	1.5.1	Recommended Phase 2 Dose Selection and Rationale	30
2	STUDY	OBJECTIVES	31
3	STUDY	ENDPOINTS	32
4	STUDY	DESIGN	33
	4.1 I	Phase 1 Dose-Escalation Stage	35
	4.1.1	Single-Agent (SA) Dose Escalation (Complete)	35
	4.1.2	FT-2102 + Azacitidine (Combination) Dose-Escalation (Complete)	36
	4.1.3	Definition of Dose-Limiting Toxicity	38
	4.1.4	Phase 1 Dose-Expansion Stage	38
	4.2 I	Phase 2 Stage	39
	4.3 I	Response Assessment	40

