4.4 Eligibility Criteria

4.4.1 Inclusion Criteria

To be considered eligible to participate in this study, a patient must meet ALL inclusion criteria listed below:

- 1. Pathologically proven AML (except acute promyelocytic leukemia with the t(15;17) translocation) or intermediate risk, high risk or very high risk MDS as defined by the World Health Organization (WHO) criteria or Revised International Prognostic Scoring System (IPSS-R) harboring IDH1-R132 mutations, and one of the following based on enrollment stage or treatment cohort:
 - a. Single Agent Phase 1 Cohorts including Dose-Escalation/ Dose-Expansion: AML/MDS either R/R to standard therapy, or for whom standard treatments are contraindicated
 - b. Combination (FT-2102 + azacitidine) Phase 1 Dose-Escalation/ Dose-Expansion (patients must meet one of the following):
 - i. Patients with AML that is either R/R to standard therapy, or for whom standard treatments are contraindicated
 - ii. Patients with MDS that is either R/R to standard therapy, or are treatmentnaïve, who are eligible for azacitidine therapy
 - c. Combination (FT-2102 + cytarabine) Phase 1 Dose-Escalation/Dose-Expansion Cohort: Patients ≥ 60 years with treatment-naïve AML for whom standard treatments are contraindicated
 - d. Phase 2 Cohort 1 (Single Agent) only: AML R/R to standard therapy
 - e. **Phase 2 Cohort 2 (Single Agent) only:** AML in morphologic CR/CRi after prior therapy (+/- HSCT) with residual IDH1-R132 mutation (≥ 0.01%) detected in the bone marrow
 - f. **Phase 2 Cohort 3 (Single Agent) only:** R/R AML/MDS that have been previously treated with FT-2102 **AND** for whom standard treatments are contraindicated
 - g. **Phase 2 Cohort 4 (FT-2102 + Azacitidine) only:** Patients < 60 years old with R/R AML/MDS with no prior hypomethylating agent therapy **AND** no prior IDH1 inhibitor therapy
 - h. **Phase 2 Cohort 5 (FT-2102 + Azacitidine) only:** R/R AML/MDS that have inadequately responded to or have progressed on prior treatment with a hypomethylating agent

- i. Phase 2 Cohort 6 (FT-2102 + Azacitidine) only: R/R AML/MDS that have been previously treated with single agent FT-2102 as their last therapy prior to study enrollment
- j. **Phase 2 Cohort 7 (Single Agent) only:** Treatment naïve AML patients for whom standard treatments are contraindicated
- k. **Phase 2 Cohort 8 (FT-2102 + Azacitidine) only:** Treatment naïve AML patients who are candidates for azacitidine as a first line treatment

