Transfusion independence, defined as the proportion of patients who have received a packed red blood cell or platelet transfusion in the eight weeks prior to first dose of FT-2102 who have a 28-day period during any point on study with no transfusion required. Additionally, the number of patients who are transfusion independent for at least 56 consecutive days will also be summarized. Percent of transfusion independence will be calculated based on the number of patients who were transfusion dependent prior to first dose of FT-2102.

For each cohort, the number and percentage of the best overall response will be presented by response category and by treatment group. Other binomial endpoints including overall response rate (CR + CRh + CRi + MLFS + PR) and rate of responses in the individual response category, will also be analyzed. Number and percentage of patients within each response category will be presented by dose/dosing schedule and visit. Clopper-Pearson 95% confidence intervals will be provided along with the responses.

Overall survival for all cohorts at landmark timepoints will be analyzed.

Time to event data will be analyzed using Kaplan-Meier (KM) methods for each cohort. The median time will be tabulated along with the 95% Brookmeyer Crowley confidence intervals. The estimated probability of survival over time will be plotted as KM curves for each cohort (or by disease type and by treatment).

Detailed considerations for all time to event variables are provided in the SAP.

Additional efficacy analyses will be specified in the SAP.

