After dose-expansion is complete for FT-2102 as a single agent and FT-2102 in combination with azacitidine, a cohort of 6 patients with AML harboring IDH1 mutation will be treated with FT-2102 in combination with cytarabine 20 mg BID for 10 days, and then cytarabine will be stopped for 18 days. Starting dose of 150 mg FT-2102 will be given twice daily in accordance with dosing schedule \times 28 days out of 28 days. Further dose-escalation of FT-2102 in combination with cytarabine will not occur beyond 150 mg BID.

If > 1 DLTs are observed at the 150 mg BID dose in combination with cytarabine, a lower dose level may be explored.

Recommended Phase 2 Dose

FT-2102 150 mg BID is the RP2D confirmed for single-agent and azacitidine combination treatment.

Phase 2

The Phase 2 portion of the study is comprised of 4 patient cohorts receiving single agent therapy, and 4 patient cohorts receiving combination therapy, defined as follows.

Single-Agent Cohorts:

- Cohort 1 (SA FT-2102): approximately 173 evaluable patients with R/R AML. To account for potential discordance between local and central mutation testing, approximately 190 patients may be enrolled into this cohort.
- Cohort 2 (SA FT-2102): approximately 53 patients with AML in morphologic CR/CRi after prior therapy (+/-hematopoietic stem cell transplantation [HSCT]) with residual IDH1-R132 mutation (> 0.01%) detected in the bone marrow.
- Cohort 3 (SA FT-2102): approximately 20 patients with R/R AML/MDS that have been previously treated with IDH1 inhibitor therapy. Patients who undergo HSCT on-study then relapse post-HSCT are allowed in this cohort.
- Cohort 7 (SA FT-2102): approximately 54 treatment naïve AML patients for whom standard treatments are contraindicated.

Azacitidine Combination Cohorts:

- Cohort 4 (FT-2102 in combination with azacitidine): approximately 20 patients with R/R AML/MDS that are naïve to prior hypomethylating therapy and IDH1 inhibitor therapy.

- Cohort 5 (FT-2102 in combination with azacitidine): approximately 20 patients with R/R AML/MDS that have inadequately responded to or have progressed on prior hypomethylating therapy.

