Time to response (TTR): TTR is the time in months between the first dose of study drug and documentation of the first overall response for patients who achieve a PR or better. This analysis will be performed only on patients who have achieved PR or better as a best overall response. Kaplan Meier analyses will not be performed; summary will be descriptive. This analysis will not be performed on Phase 2 Cohort 2, as it is not applicable since patients enter the study already in response.

Duration of CR/CRh (DCR/CRh): DCR/CRh is the time in months between documentation of the first CR or CRh until the date of relapse or death, whichever is earlier. Patients will be censored as per Table 1. DCR/CRh will only be calculated for patients who achieve a CR or CRh as the best response.

Duration of complete remission (DCR): DCR is the time in months between documentation of the first CR until the date of relapse or death, whichever is earlier. Patients will be censored as per Table 1. DCR will only be calculated for patients who achieve a CR as the best response.

Duration of overall response (DOR): Duration of overall response will be calculated similarly to DCR but will assess the time in months between documentation of the first response of PR or better until the date of relapse, death, whichever is earlier. Patients will be

censored as per Table 1. This analysis will not be performed on Phase 2 Cohort 2, as it is not applicable since patients enter the study already in response.

Patients who respond and stop FT-2102 to undergo HSCT will continue to be followed until relapse. Duration of response endpoints (DRC/CRh, DCR, DOR) for these patients will encompass time between HSCT and relapse ordeath. For patients with no report of relapse by the end of the follow-up data collection, duration of response (DCR/CRh, DCR, DOR) will be censored as per Table 1.

A separate sensitivity analysis will be conducted for duration of response of Phase 2, Cohort 1 patients, which analyzes duration of response as described above, but for those patients who have enrolled under Phase 2 Cohort 2 due to MRD positivity, the duration of response will be the total duration of response experienced in Cohort 1 and Cohort 2 together.

An additional sensitivity analysis will be performed on DCR/CRh, DCR, and DOR in which HSCT will be handled as the end of response.

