The overall survival and event-free survival analyses will be based on patients in the FAS. All other efficacy analyses will be based on patients in the EE analysis set as the primary analysis, with selected analyses on the FAS and PP analysis set as supportive. The following table indicates the analysis sets to be analyzed for each endpoint.

		A	alysis S	et
Endpoint	Patients Analyzed	EE*	FAS	PP*
CR/CRh Rate,				
DCR/CRh, TTCR/CRh	AML only	Х	Х	Х
CRR, DCR, TTCR	Each disease group separately	х	Х	Х
ORR, DOR, TTR	Each disease group separately	х	Х	х
Best overall Response	Each disease group separately	х	Х	Х
4-month RFS Rate	Phase 2 Cohort 2 only		Х	
RFS	Phase 2 Cohort 2 only		Х	
EFS, OS	All patients combined		Х	
TI	All patients combined	х	х	

*EE and PP analyses will only be performed for IA2.

CR/CRh rate will be analyzed for all cohorts except Phase 2 Cohort 2. For Phase 2 Cohort 1, to test the hypothesis that the CR/CRh rate is greater than 15%, a 1-sided exact test for a binomial proportion will be performed. If the exact one-sided p-value is less than 0.0245, the alternative hypothesis will be accepted. This is equivalent to at least 36 CR/CRh responses of 173 EE patients.

For Phase 2, Cohorts 3, 4, and 5 test the hypothesis that the 85% confidence interval for the CR/CRh rate does not include 10%. If there are 5 or more CR/CRh responses of the 20 patients in these cohorts, the 85% confidence interval will be greater than 10%, and the alternative hypothesis that the response rate is greater than 10% will be accepted.

Phase 2 Cohorts 6, 7, and 8 are Simon 2-Stage designs and the primary efficacy endpoint will be evaluated via the number of CR/CRh responses stipulated in the design criteria described in Section IV.C.

The number and proportion of patients achieving CR/CRh response will be reported by cohort from the binomial proportion, along with Clopper-Pearson 95% confidence interval for AML and MDS patients respectively. Appendix 2 provides the SAS code.

For Phase 2 Cohort 1, a sensitivity analysis will be performed on the CR/CRh rate in which Atkinson and Brown confidence intervals will be calculated.

4-Month RFS, BOR, ORR, TI: The proportional endpoints listed here will be summarized as the number and percentage of patients within each category, and will be presented by cohort along with Clopper-Pearson 95% confidence intervals. The 4-month RFS endpoint will be analyzed for Phase 2 Cohort 2 only.

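### Cohort 2 patients enter in CR/CRi, yet ORR and best overall response are still presented for that cohort, so a kept entry remission counts as an overall response

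*SAP*

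**What the plan says.** **Entry.** Protocol 4.4.1 (criterion 1e) admits to Cohort 2 patients with "AML in morphologic CR/CRi after prior therapy (+/- HSCT) with residual IDH1-R132 mutation" in the bone marrow. SAP IV.A plans "approximately 53 patients with AML in morphologic CR/CRi after prior therapy".

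**Where the SAP makes an exception.**
- For time to response (SAP XI.A): "This analysis will not be performed on Phase 2 Cohort 2, as it is not applicable since patients enter the study already in response". The same reason is repeated for duration of overall response.
- The CR/CRh rate (SAP XI.B) "will be analyzed for all cohorts except Phase 2 Cohort 2".

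**Where it does not.**
- SAP XI.B, in the paragraph covering 4-month RFS, BOR, ORR and transfusion independence: "The proportional endpoints listed here will be summarized as the number and percentage of patients within each category, and will be presented by cohort", with Clopper-Pearson 95% intervals. Only 4-month RFS is tied to a particular cohort there.
- The protocol synopsis (Efficacy Analyses) states that "the ORR will be calculated for each cohort". Protocol 9.2.4.3 adds: "For each cohort, the number and percentage of the best overall response will be presented by response category".
- CRR, TTCR/CRh, TTCR, DCR/CRh and DCR (SAP XI.A) are defined by the response reached, with no mention of Cohort 2. For example: "DCR/CRh will only be calculated for patients who achieve a CR or CRh as the best response".

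All of these run on the FAS, which includes Cohort 2. The single-agent efficacy table shell in SAP Appendix 3 gives Cohort 2 a column beside Cohorts 1, 3 and 7.

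**The concern.** Cohort 2's entry condition is also a response condition. ORR for AML counts CRm, CRc, CR, CRh, CRi, MLFS and PR. BOR is the best category recorded on study, with no reference to baseline, and AML responses need no minimum duration (protocol 4.3, Table 3 footnote, and Appendix 7). One on-study marrow showing that the remission brought in from prior therapy is still there therefore makes the patient an overall responder.

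The SAP accepts this reasoning for TTR and DOR but does not carry it to ORR, the rate on which those two endpoints depend. The resulting figure would stand as a secondary efficacy estimate with an exact interval, next to cohorts with active disease. EE and PP analyses are produced only for the second interim analysis of Cohort 1, so the final report relies on FAS tables, where the Cohort 2 column appears.

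**Working it through.** **1. The plan's own figure.** Cohort 2 design (SAP IV.C, protocol 9.2.2.2): stop if 9 or fewer of 11 are relapse-free; reject if 48 or more of 53 are; null 80%, alternative 94%.

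P(reject) = Σ over x = 10, 11 of P(X₁ = x; 11, p) × P(X₂ ≥ 48 − x; 42, p)

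- At p = 0.80: 0.0248 (stated 0.025)
- At p = 0.94: 0.805 (stated 80%)

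The design reproduces. It uses 4-month RFS only, so nothing below alters it.

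**2. ORR when the drug adds nothing.** Inputs:
- 4-month RFS of 80% (null) and 94% (alternative), from the design.
- First on-study marrow for Cohort 2 at C2D1 (protocol 4.3), day 29 with 28-day cycles.
- Four months taken as 120 days, the study day that the SAP uses for late 4-month assessments.
- Assumptions: constant hazard of relapse or death; every patient still in remission has an evaluable marrow.

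Share still in remission at C2D1 = (4-month RFS)^(29/120)

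| 4-month RFS | Share at C2D1 | Of 53 | Exact 95% interval at the rounded count |
|---|---|---|---|
| 80% | 0.80^(29/120) = 0.9475 | 50.2, about 50 | 50/53 = 94.3%: 84.3% to 98.8% |
| 94% | 0.94^(29/120) = 0.9852 | 52.2, about 52 | 52/53 = 98.1%: 89.9% to 99.95% |

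With 28 days and four months of 30.4375 days, the null figure is 0.80^(28/121.75) = 0.950, so the choice of day count does not matter.

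The two hypotheses are 94 − 80 = 14 percentage points apart on 4-month RFS, but 98.5 − 94.75 = about 3.8 points apart on ORR, or two patients in 53.

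**3. How far this depends on constant hazard.** If 80% are relapse-free at four months, at least 80% were so at C2D1, whatever the hazard shape. The null ORR then lies between 80% (0.80 × 53 = 42.4, about 42 of 53) and 100%. It is high in every case.

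**4. CRR.** The share of patients entering in CR rather than CRi is not given. With no conversion on study, the null CRR is that share × 0.9475:

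| Assumed share entering in CR | Null CRR |
|---|---|
| 30% | 28% |
| 50% | 47% |
| 70% | 66% |

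**5. Time and duration endpoints.** For a patient entering in CR, TTCR is the wait until the first scheduled marrow, and DCR starts at that visit rather than when remission began. The same holds for the CR/CRh versions in a patient who enters in CR or already meets the CRh counts. It does not hold for a patient entering in CRi below those counts, who must first improve.

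**The case against.** **Only ORR and BOR are explicitly instructed for each cohort.** This stands. For the other five endpoints the concern rests on a missing exclusion. The analysis-set table in SAP XI.B puts the CR/CRh rate, DCR/CRh and TTCR/CRh in one row, and the rate is not analysed in Cohort 2, so the authors may have meant the exclusion to cover the row. The text does not say so, and CRR, DCR and TTCR sit in another row.

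**The SAP limits more than three outputs.** Kaplan-Meier curves for DCR/CRh, DCR and DOR are planned for Phase 2 Cohort 1 only. This also stands, although medians and landmark estimates are still specified by cohort.

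**Some Cohort 2 responses are real changes.** A reader might infer that no Cohort 2 response can be new. The documents do not support that. Entry requires residual IDH1-R132 mutation, while CRm requires CR with undetectable IDH1-mutant MRD, so reaching CRm is a change on study. So is CRi to CR or CRh. The BOR table is where such changes would show.

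**The consequences are small.** Secondary outputs are descriptive (SAP VI.H). The EE set contains only Cohort 1, so the EE-based ORR subgroups and forest plots exclude Cohort 2. The Phase 2 efficacy shells do not pool Cohort 2 with other cohorts. No test or stopping rule uses its ORR. All of this stands and limits the weight of the point, but it does not make the estimate meaningful.

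**Conclusion.** The point holds for ORR and for BOR presented as response. Followed as written, the plan yields a Cohort 2 ORR of about 95% for a drug with no effect (about 50 of 53, lower bound 84%) and about 98.5% at the target effect. This assumes a constant hazard and an evaluable C2D1 marrow; without the constant hazard, the null figure is still at least 80%. Such a rate mainly reflects prior therapy and barely separates the two hypotheses.

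For CRR, TTCR/CRh, TTCR, DCR/CRh and DCR, the finding is an unstated exclusion that needs settling. The artefact there falls mainly on patients who enter in CR or, for the CR/CRh endpoints, already meet CRh.

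A reader might also infer that the Cohort 2 conclusion is compromised. It is not: its primary test is on 4-month RFS and keeps its stated error rate and power.

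**What to change.** In SAP XI.A, extend the exclusion already written for TTR and DOR: ORR, CRR, TTCR/CRh, TTCR, DCR/CRh and DCR are not reported for Phase 2 Cohort 2, because its patients are in remission at entry. Repeat the exception in the BOR/ORR paragraph of SAP XI.B, and note it as a departure from the each-cohort wording in the protocol synopsis and 9.2.4.3.

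Keep deriving BOR for Cohort 2. EFS treatment failure depends on it, and the transfusion-independence and quality-of-life summaries are broken down by it. Present it for this cohort only as a cross-tabulation of entry category by best on-study category, so that conversions such as CRi to CR/CRh or CR to CRm are visible as changes. RFS, 4-month RFS, EFS and OS stay as planned.

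The cost is a few sentences and one small table in place of several cells. Sample size, alpha, power and data collection do not change.

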Cohort 2 (patients with AML with persistent IDH1-R132 mutation + bone marrow demonstrating morphologic CR/CRi after prior therapy +/- HSCT): A Simon optimal two-stage design will be used. The null hypothesis that the true 4-month RFS rate is 80% will be tested against a one-sided alternative. In the first stage, 11 patients will be evaluated. If 9 or fewer of the first 11 patients are relapse-free at 4 months, the study will be stopped. Otherwise, 42 additional patients will be accrued, for a total of 53 patients. The null hypothesis will be rejected if 48 or more of these 53 patients are event-free at 4 months. This design yields a 1-sided type I error rate of 0.025 and power of 80% when the true 4-month RFS rate is 94%.

Cohorts 3-5 (patients with AML/MDS harboring IDH1-R132 mutations that are R/R to prior IDH1 inhibitor therapy; or naïve to hypomethylating and IDH1m inhibitor treatments; or R/R to prior hypomethylating therapy): A single-stage design with 20 patients will be used. If 4 or more complete responses are observed in these 20 patients, the lower bound of a one-sided 85% confidence interval based on an exact binomial distribution will be greater than 10%, thus supporting the hypothesis that the true complete response rate is greater than 10%.

Cohort 6 (patients with AML/MDS harboring IDH1-R132 mutations that are R/R to immediately prior SA IDH1 inhibitor therapy): A Simon's optimal two-stage design will be used. The null hypothesis that the true complete response rate is 15% will be tested against a one-sided alternative. In the first stage, 14 patients will be evaluated. If there are 2 or fewer complete responses in the first 14 patients, the study will be stopped. Otherwise, 30 additional patients will be accrued for a total of 44 patients. The null hypothesis will be rejected if 11 or more complete responses are observed in these 44 patients. This design yields a 1-sided type I error rate of 0.05 and power of 80% when the true complete response rate is 32%. The probability that the trial will be stopped at the end of the first stage if the true complete response rate is 10% is 0.65.

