9.2.4.3 Antileukemic and Antimyelodysplastic Activity

All analysis in the section will be based on patients in the EE Set as the primary analysis, with additional analyses on the FAS, and in some cases the PP Set as supportive.

Primary Efficacy Endpoints and Hypotheses

CR/ CRh Rate

The primary efficacy endpoint for all Phase 2 cohorts, with the exception of Cohort 2, is the CR/CRh rate (defined as bone marrow blasts < 5% with complete (CR) or partial (CRh) hematologic recovery; see Appendix 7 and Appendix 8 for complete definition). The CR/CRh rate will be calculated and presented together with the Clopper-Pearson 95% confidence interval for each cohort.

For Phase 2, Cohort 1, to test the hypothesis that the complete response rate is greater than 15%, a 1-sided exact test for a binomial proportion will be performed. If the exact 1-sided p-value is less than 0.023, the alternative hypothesis will be accepted. This is equivalent to at least 36 CR/CRh responses of 173 EE patients.

For Phase 2, Cohorts 3, 4, and 5 test the hypothesis that the 85% confidence interval for the complete response rate does not include 10%. If there are 5 or more complete responses of the 20 patients in these cohorts, the 85% confidence interval will be greater than 10%, and the alternative hypothesis that the response rate is greater than 10% will be accepted.

Phase 2 Cohorts 6, 7, and 8 are Simon 2-Stage designs and the primary efficacy endpoint will be evaluated via the number of CR/CRh responses stipulated in the design criteria described in Section 9.2.2.

4-Month RFS

The primary endpoint for Phase 2 Cohort 2 is the 4-Month RFS. This will be evaluated by a Simon 2-Stage design described in Section 9.2.2, testing the null hypothesis that the 4-month RFS is < 80%. It is defined as the proportion of patients who have not relapsed or died on or before their 4-month response evaluation. If a patient does not receive a disease response assessment at their 4-month visit but has a subsequent disease response assessment on or after study day 120 that shows non-progression/ non-relapse, they will be evaluated as having achieved 4-month RFS.

Secondary Efficacy Endpoints

CRi, MLFS, Marrow CR, and PR definitions will be derived from the IWG response criteria (see Section 4.3, Appendix 7 and Appendix 8) for AML (2003) and MDS (2006) based on investigator's assessment.

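### Cohorts 2, 6, 7 and 8 use Simon two-stage tests but report single-stage Clopper-Pearson intervals, so at the boundary counts a declared success could sit beside an interval that contains the null

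*SAP*

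**What the plan says.** The designs are in Protocol 9.2.2.2 and SAP IV.C. Cohorts 2, 6, 7 and 8 each have a first stage with a futility stop and a final rejection count. The nominal one-sided error is 2.5%, except in Cohort 6, where it is 5%.

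The intervals are in SAP XI.B:

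- **Cohorts 6 to 8.** The number and proportion with CR/CRh "will be reported by cohort from the binomial proportion, along with Clopper-Pearson 95% confidence interval for AML and MDS patients respectively". Protocol 9.2.4.3 also has the CR/CRh rate "presented together with the Clopper-Pearson 95% confidence interval for each cohort".
- **Cohort 2.** The 4-month RFS rate, with other proportions, "will be presented by cohort along with Clopper-Pearson 95% confidence intervals".
- **Cohort 1 only.** "For Phase 2 Cohort 1, a sensitivity analysis will be performed on the CR/CRh rate in which Atkinson and Brown confidence intervals will be calculated".

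SAP Appendix 2.A gives exact-binomial code run by cohort, with nothing for stages. For Cohorts 6 to 8 the decision does not use the interval: the endpoint is "evaluated via the number of CR/CRh responses stipulated in the design criteria". Cohort 2 is likewise judged by its count rule.

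**The concern.** A Simon rejection count is valid at its nominal level partly because some paths to that count are cut off by the stage 1 stop. Clopper-Pearson limits treat all patients as one fixed sample and ignore the stop. Test and interval therefore rest on different sampling models, and near the boundary they can disagree.

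Cohort 6 also has a mismatch of level. A two-sided 95% interval corresponds to a one-sided 2.5% test, while the cohort tests at 5%.

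At stake is how a primary result reads. A report could state that the null rate was rejected and print an interval that includes it, with no rule agreed beforehand on which one speaks for the cohort.

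**Working it through.** **Inputs** (Protocol 9.2.2.2, SAP IV.C)

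| Cohort | Stage 1: stop if | Reject if | Null p0 | Alternative p1 | Nominal one-sided error |
|---|---|---|---|---|---|
| 2 | ≤ 9 of 11 | ≥ 48 of 53 | 80% | 94% | 0.025 |
| 6 | ≤ 2 of 14 | ≥ 11 of 44 | 15% | 32% | 0.05 |
| 7 | ≤ 5 of 17 | ≥ 20 of 54 | 25% | 45% | 0.025 |
| 8 | ≤ 2 of 7 | ≥ 12 of 28 | 25% | 55% | 0.025 |

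**Step 1: reproduce the designs.** With n1 and n the stage 1 and total sizes, r1 the stopping count and r the rejection count,

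P(reject | p) = Σ over x1 > r1 of Bin(x1; n1, p) × P(X2 ≥ r − x1; n − n1, p).

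Exact error / power: Cohort 2 0.0248 / 80.5%; Cohort 6 0.0457 / 80.1%; Cohort 7 0.0245 / 80.4%; Cohort 8 0.0208 / 81.1%. The stated designs hold, with the stated error read as a cap.

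**Step 2: the planned interval at the rejection count.** The Clopper-Pearson lower limit is the 0.025 quantile of Beta(x, n − x + 1). The upper limit is the 0.975 quantile of Beta(x + 1, n − x).

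| Cohort | Count | Clopper-Pearson 95% | Null | Single-stage one-sided p | Two-stage p |
|---|---|---|---|---|---|
| 2 | 48/53 = 90.6% | 79.3–96.9% | 80% | 0.0322 | 0.0248 |
| 6 | 11/44 = 25.0% | 13.2–40.3% | 15% | 0.0566 | 0.0457 |
| 7 | 20/54 = 37.0% | 24.3–51.3% | 25% | 0.0334 | 0.0245 |
| 8 | 12/28 = 42.9% | 24.5–62.8% | 25% | 0.0294 | 0.0208 |

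All four intervals contain the null.

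**Step 3: how far the conflict reaches.** The 95% interval excludes the null from 49/53, 13/44, 21/54 and 13/28 upward. The affected counts are therefore 48; 11 and 12 (lower limit 14.96% at 12/44); 20; and 12.

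**Step 4: how often.** The two-stage probability of the affected counts at p1 is 8.3%, 15.1%, 3.8% and 4.4%. As a share of successful outcomes (divide by power): 8.3/80.5 = 10.3%, 15.1/80.1 = 18.9%, 3.8/80.4 = 4.7%, 4.4/81.1 = 5.4%.

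**Step 5: coverage.** Clopper-Pearson coverage was computed under the actual two-stage sampling for true rates from 5% to 98%, using n1 as denominator after a stage 1 stop. The minimum is about 93.4% in Cohort 6, 94.0% in Cohort 7 and 94.3% in Cohort 8. It stays above 95% in Cohort 2.

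**Step 6: a design-adjusted interval.** Invert the two-stage tail probabilities, ranking stage 1 stops below all stage 2 outcomes. The 95% intervals at the rejection count are:

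- Cohort 2: 80.03–97.9%
- Cohort 7: 25.05–56.4%
- Cohort 8: 25.6–71.2%
- Cohort 6: 13.6–44.1%

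The first three exclude their nulls; Cohort 6 does not. At 11/44 the Clopper-Pearson 90% interval (14.7–38.0%) also contains 15%, while the two-stage 90% interval (15.2–40.8%) excludes it. Both changes are needed there. At 12/44 the two-stage p is 0.0219, below 0.025, so the two-stage 95% interval already excludes 15%.

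**The case against.** The case on the other side is substantial.

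- **No decision depends on the interval.** The count rules decide, and the two-stage error and power are as designed. A reader might infer that type I error is inflated or that success could be wrongly declared. Step 1 shows otherwise.
- **The conflict is confined to the boundary.** In Cohorts 2, 7 and 8 it is a single count, and the lower limit falls short of the null by only 0.5 to 0.7 percentage points. A reader might infer that any success would be contradicted. It could be, but only at the counts in step 3.
- **Clopper-Pearson is not invalid here.** The largest loss of coverage is 95 − 93.4 = 1.6 points. Calling the plan wrong as written would overstate this.
- **Cohort 6 is partly a question of level.** A uniform 95% reporting level is defensible. This stands in part: at 11/44 a 90% Clopper-Pearson interval still contains the null, so level is not the whole cause.
- **The protocol prescribes Clopper-Pearson** for the CR/CRh rate in each cohort. Making it supplementary would depart from Protocol 9.2.4.3, whereas adding a second interval does not.
- **The Cohort 6 denominator may differ from 44.** The cohort enrols AML and MDS and may exceed 44 (Protocol 4.2). SAP XI.A does not calculate CR/CRh for MDS, and the SAP XI.B table limits it to AML.

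None of this explains why the one design-adjusted interval in the SAP stops at Cohort 1.

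**Conclusion.** The point holds as a matter of consistency between test and interval. The planned intervals for the primary endpoints of four two-stage cohorts ignore the stage 1 stop. In Cohort 6 they are also at a level that does not match the test. The consequence is a possible contradiction in the report, with probability between 3.8% and 15.1% at the design alternatives, and slightly low coverage in Cohorts 6 to 8. It is not a flaw in the tests.

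The figures assume exactly 53, 44, 54 and 28 patients, with stage 1 sizes as planned and every patient counted in the primary rate. The probabilities apply at the design alternatives only. The adjusted limits assume the ordering in step 6; the SAP names Atkinson and Brown without setting out an ordering.

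**What to change.** In SAP XI.B, extend the Atkinson and Brown interval to the CR/CRh rate in Cohorts 6, 7 and 8 and to the 4-month RFS rate in Cohort 2. Report it beside the Clopper-Pearson 95% interval, which stays as the protocol has it. Specify:

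- that the interval uses the realised stage 1 and total sizes, which matters most for Cohort 6;
- that Cohort 6 also gets the two-sided 90% version matching its one-sided 5% test (15.2–40.8% at 11/44);
- that the count rule in SAP IV.C governs the decision, repeated as a table footnote;
- the ordering of outcomes, with code added to Appendix 2.

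Label: cheap improvement. The cost is a second interval per cohort (and a 90% version in Cohort 6) and a little programming. No new data, change of design or change to any decision rule is needed. Fixing the choice before results are known avoids picking an interval afterwards.
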